12.1.2. Secondary Endpoints

Secondary endpoints will be to evaluate mesh-related complications and subject reported outcomes as safety endpoints between baseline and 36 months:

1. Incidence of mesh erosion
2. Incidence of mesh exposure
3. Incidence of de novo dyspareunia
4. Improvement in subject specific outcomes at 36 months compared to Baseline (pelvic floor symptoms (PFDI-20), QOL (PFIQ-7), sexual functioning (PISQ-12), TOMUS pain scale)
5. Assessment of subject's level of improvement, measured by the Patient Global Impression of Improvement for Prolapse (PGI-I for Prolapse)
6. Absence of re-intervention or re-surgery for recurrence or persistence of POP or mesh exposure/erosion
7. Surgical success based on the following composite outcome:
 - a. Subjective success: patient denies symptoms of vaginal bulging per PFDI-20 question 3, answering "no" or "yes" but "Not at all" bothersome (<2)
 - b. Anatomic success (in the operated compartment):
 - Anterior Segment: No anterior prolapse at or beyond the hymen or POP-Q point Ba<0
 - Apical Segment: The vaginal apex does not descend more than one-half into the vaginal canal (i.e. POP-Q point C < 1/2 TVL) for multi-compartment prolapse or POPQ point C < 0 for single compartment apical prolapse.
 - c. No retreatment for POP: No additional surgical treatment for POP in the segment(s) of the vagina treated at the index surgery or no pessary use since index surgery
8. Device or procedure-related incidence of the following: pelvic pain, infection, vaginal shortening, atypical vaginal discharge, neuromuscular problems, vaginal scarring, de novo vaginal bleeding, fistula formation and/or de novo voiding dysfunction

Definitions for the above listed adverse events are included in Section 21.2 (Definitions and Classifications). Rates of incidence for the adverse events will be stratified by primary or recurrent prolapse in both treatment groups.

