Primary Effectiveness Endpoint(s)	
The primary endpoint of the study is to achieve superiority of mesh over native tissue repair at 36 months as compared to baseline. Success will be based on a composite of objective and subjective measures, and subjects will be considered a surgical success if each of the three criteria is met:
 
 1. Objective success is achieved by the subject having an anatomic outcome defined as the leading edge of prolapse at or above the hymen in the operated compartment: 
 • Anterior segment: Leading edge of anterior prolapse is at or above the hymen or POP-Q point Ba \leq 0. • Apical segment: The vaginal apex does not descend more than one-half into the vaginal canal (i.e. POP-Q point C < -1/2 TVL) for multi-compartment prolapse or POPQ point C \leq 0 for single compartment apical prolapse. 2. Subjective success is achieved if the patient denies symptoms of vaginal bulging per PFDI-20 question 3, answering “no” or “yes” but “Not at all” bothersome (<2). 3. No retreatment for POP: no additional surgical treatment for POP in the segment(s) of the vagina treated at the index surgery or no pessary use since index surgery (i.e., ‘treated segment’ refer to the target compartment).
Primary Safety Endpoint(s)	A co-primary endpoint of the study is to achieve non-inferiority of mesh to native tissue repair for safety by comparing rates of serious device or serious procedure-related complications between baseline and the 36 month time point. Serious injury is defined per 21 CFR 803.3, i.e., life threatening, results in permanent impairment of a body function or permanent damage to a body structure, or injury or illness that requires medical or surgical intervention to preclude impairment of a body function or permanent damage to a body structure.

Postmarket Study PS130044: A Prospective, Non-Randomized, Parallel Cohort, Multi-center Study of Uphold LITE vs. Native Tissue for the Treatment of Women with Anterior/Apical Pelvic Organ Prolapse	

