7.1. Primary Endpoints

The primary endpoint of the study is to achieve superiority of mesh over native tissue repair at 36 months as compared to baseline.

Success will be based on a composite of objective and subjective measures, and subjects will be considered a surgical success if each of the three criteria is met:

1. Objective success is achieved by the subject having an anatomic outcome defined as the leading edge of prolapse at or above the hymen in the operated compartment:
 - Anterior segment: Leading edge of anterior prolapse is at or above the hymen or POP-Q point Ba \leq 0.

- Apical segment: The vaginal apex does not descend more than one-half into the vaginal canal (i.e. POP-Q point C < -1/2 TVL) for multi-compartment prolapse or POPQ point C ≤ 0 for single compartment apical prolapse.
2. Subjective success is achieved if the patient denies symptoms of vaginal bulging per PFDI-20 question 3, answering “no” or “yes” but “Not at all” bothersome (<2).
 3. No retreatment for POP: no additional surgical treatment for POP in the segment(s) of the vagina treated at the index surgery or no pessary use since index surgery (i.e., ‘treated segment’ refer to the target compartment).

Additionally, a co-primary endpoint of the study is to achieve non-inferiority of mesh to native tissue repair for safety by comparing rates of serious device or serious procedure complications between baseline and the 36 month time point. Serious injury is defined per 21 CFR 803.3, i.e., life threatening, results in permanent impairment of a body function or permanent damage to a body structure, or injury or illness that requires medical or surgical intervention to preclude impairment of a body function or permanent damage to a body structure.

7.2. *Secondary Endpoints*

The secondary endpoints of the study include assessments of complications and subject reported outcomes:

1. Incidence of mesh erosion
2. Incidence of mesh exposure
3. Incidence of de novo dyspareunia
4. Improvement in subject-related outcomes at 36 months compared to Baseline ((pelvic floor symptoms (PFDI-20), QOL (PFIQ-7), sexual functioning (PISQ-12) TOMUS pain scale)
5. Assessment of subject’s level of improvement, measured by the Patient Global Impression of Improvement for Prolapse (PGI-I for Prolapse)
6. Absence of re-intervention and re-surgery for recurrence of POP, persistence of disease, or mesh exposure/erosion
7. Surgical success based on the following composite outcome:

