 - a. Subjective success: patient denies symptoms of vaginal bulging per PFDI-20 question 3, answering “no” or “yes” but “Not at all” bothersome (<2)
 - b. Anatomic success (in the operated compartment):
 - Anterior Segment: No anterior prolapse at or beyond the hymen or POP-Q point Ba<0
 - Apical Segment: The vaginal apex does not descend more than one-half into the vaginal canal (i.e. POP-Q point C < 1/2 TVL) for multi-

compartment prolapse or POPQ point C < 0 for single compartment apical prolapse.

- c. No retreatment for POP: No additional surgical treatment for POP in the segment(s) of the vagina treated at the index surgery or no pessary use since index surgery
8. Incidence of the following device or procedure-related AEs: pelvic pain, infection, vaginal shortening, atypical vaginal discharge, neuromuscular problems, vaginal scarring, de novo vaginal bleeding, fistula formation and/or de novo voiding dysfunction

8. Study Design

This study is a prospective, non-randomized, parallel cohort, multi-center study conducted in partnership with the AUGS PFD Registry.

The primary endpoint will be assessed once all per protocol subjects have completed the 36 month study visit. All per protocol subjects will be followed to month 36, until study completion, or until discontinuation prior to month 36. All study procedures will be standardized for uniformity. Physicians will have to provide documentation of a minimum of 10 procedures (i.e., native tissue repair procedure or Uphold/Uphold LITE procedure) prior to participation in order to document competency and experience. Physician training, specialty, and site procedure location (such as outpatient in private-practice, institutional hospital, etc.) will be recorded.

All efforts will be made to ensure all follow-up anatomic measurements (POP-Q) will be assessed by a healthcare provider to reduce treating surgeon bias on outcomes after the index procedure. In the event the treating surgeon is the only qualified healthcare provider at the site trained in POP-Q assessments, the follow-up anatomic measurements will be performed by the treating surgeon.

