9.2. Inclusion Criteria

Subjects who meet all of the following criteria may be given consideration for inclusion in this clinical investigation, provided no exclusion criterion (see Section 9.3) is met.

1. Subject is female
2. Subject is ≥ 18 years of age
3. Subject has pelvic organ prolapse with the leading edge at or beyond the hymen. At or beyond the hymen is defined as POP-Q scores of $Ba \geq 0$ (for prolapse of the anterior compartment alone) or $C \geq 0$ (for prolapse of the Apical compartment alone) or $C \geq -1/2$ TVL and $Ba \geq 0$ (for multi-compartment prolapse that includes the anterior and apical compartments)
4. Subject reports of a bothersome bulge they can see or feel per PFDI-20, question 3 response of 2 or higher (i.e. responses of “somewhat”, “moderately”, or “quite a bit”)
5. Subject or subject’s legally authorized representative must be willing to provide written informed consent
6. Subject is willing and able to comply with the follow-up regimen

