⁵Assessment of Risk Factors includes menopausal status, estrogen use, age, smoking, diabetes status, BMI, hysterectomy status, concomitant procedures, surgeon training and experience.

⁶All serious and non-serious device, procedure, and pelvic floor-related events, any other relevant events pertaining to the pelvic region, and any events resulting in death will be collected.

⁷Every effort should be made to do the follow-up visit within the window; however, if this is not possible, the site should attempt to complete the visit as soon as possible but before the next visit window opens. Follow-up visits will be considered missed once the visit window for the next follow-up visit opens. For the Month 36 visit, the visit is not considered missed until the last day of the visit window.

If a subject requires a re-surgery during the study, please refer to the reduced table below for follow-up assessments. Subjects undergoing re-interventions (non-surgical) continue with the study schedule as noted in Table 11.1-1. Additional data will be collected on subjects requiring a re-surgery, including a second procedure, mesh removal (as applicable), and second hospital discharge. All subjects who are re-operated on will continue with their follow-up schedule until 36 months post their initial study procedure.

Table 11.1-2: Data Collection Schedule for Subjects Requiring a Re-Surgery

Procedure/Assessment	Screening/ Enrollment Visit	Pre- Operative/ Baseline Visit	Surgery	Discharge	Post-Operative Follow-up Visits (± 4 Weeks)				
					Month 2 Visit (± 4 Weeks)	Re-Surgery	Discharge	Next Scheduled Follow-up Visit (-4/+12 weeks)	Month 36 Visit** (-4/+12 weeks)
Informed Consent	X							After a re-surgery, subjects will return to the clinic on the date of their next regular study visit per the Schedule of Events table above. Subjects will continue to return for all scheduled Follow-up Visits until 36 months post their initial study procedure.	
Inclusion/Exclusion Criteria Review	X								
Demographics		X							
Urine Pregnancy Test	X	X							
Physical Examination		X							
Medical History ¹		X							
Pelvic Exam with vaginal length measurement		X			X				X
Assessment of infection (vaginal, bladder)				X	X		X		X
Prolapse Grading (POP-Q Scoring)		X			X				X
PFDI-20 (Pelvic Floor Symptoms)		X			X				X
PFIQ-7 (Quality of Life)		X							X
PISQ-12 (Sexual Functioning)		X							X
PGI-I for Prolapse (Patient Improvement)									X
TOMUS Pain Scale		X			X				X

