11.4.7. Months 6, 12, 18, 24, 36 Visits (-4/+12 weeks)

- Pelvic exam with vaginal length measurement
- Assessment of infection (vaginal, bladder)
- Prolapse grading (POP-Q Scoring)
- Assessment of pain (TOMUS pain scale) and analgesic intake
- PFDI-20
- PFIQ-7
- PISQ-12

- PGI-I for Prolapse
- SSQ-8 for surgical satisfaction (Months 6, 12, 24, 36 only)
- EQ-5D for health status (Months 12, 24, 36 only)
- Assessment of adverse events (device, procedure, or pelvic floor related)
- Assessment of risk factors
- Study completion (Month 36 only)

All subjects who have completed the study surgery and discharge will proceed to be followed through the above-outlined study visits to Month 36 where the primary endpoint analysis will be achieved when the last subject completes this visit. All subjects completing the Month 36 visit will be considered to have completed the study.

11.5. *Re-Intervention/Re-Surgery*

It is the intention of this study to demonstrate an improvement in anterior/apical pelvic organ prolapse through clinical effectiveness of a transvaginal prolapse repair kit. However, it is recognized that during the course of the study, there is a possibility subjects may require a medical re-intervention for events including but not limited to failed prolapse repair, persistence of prolapse symptoms, or a mesh or procedure-related complication. A re-intervention may include surgical or non-surgical treatments and can occur for a medical complication or for prolapse recurrence. For the purpose of this study surgical interventions shall be classified as “re-surgery” and non-surgical interventions shall be classified as “re-interventions”. Analyses will be performed to compare the rate of office-based interventions and of surgical interventions for medical complications and for prolapse recurrence in both treatment groups.

Non-surgical interventions (re-interventions) are defined as office-based procedures and do not involve an operating room procedure. Examples of non-surgical interventions may include but are not limited to an office visit to trim exposed mesh or suture in the vagina, a pessary, or physical therapy to treat procedural complications or persistent prolapse symptoms. Data on non-surgical interventions will be captured in the CRFs. Subjects will continue to be followed per the regular study visit schedule.

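### The secondary composite's apical threshold lacks its minus sign, and the retreatment criterion in both composites is joined by *or*, so its scoring is ambiguous

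*Combined protocol and SAP*

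**What the plan says.** **Apical threshold.** The secondary surgical-success composite (item 7b) is defined in the synopsis, 7.2 and 12.1.2. All three give an unsigned half-TVL threshold for multi-compartment prolapse: "i.e. POP-Q point C < 1/2 TVL) for multi-compartment prolapse" in 12.1.2, and likewise "i.e. POP-Q point C < 1/2 TVL) for multi" in 7.2. The words just before the inequality require the apex to come no further than halfway down the canal. The primary composite (synopsis and 7.1) attaches the same words to a negative threshold: "i.e. POP-Q point C < -1/2 TVL) for multi-compartment prolapse". Inclusion criterion 3 (synopsis and 9.2) admits subjects with C at or above -1/2 TVL and Ba at or above 0 "for multi-compartment prolapse that includes the anterior and apical compartments".

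**Retreatment.** Criterion 3 of the primary composite (synopsis and 7.1) requires "no additional surgical treatment for POP in the segment(s) of the vagina treated at the index surgery or no pessary use since index surgery". Item 7c of the secondary composite (synopsis, 7.2 and 12.1.2) has the same construction: "No additional surgical treatment for POP in the segment(s) of the vagina treated at the index surgery or no pessary use since index surgery". In all five places the criterion is headed as the absence of retreatment for POP. Section 11.5 gives as examples of non-surgical re-intervention "an office visit to trim exposed mesh or suture in the vagina, a pessary, or physical therapy". Section 11.1 keeps re-operated women under observation: "All subjects who are re-operated on will continue with their follow-up schedule until 36 months post their initial study procedure".

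**The concern.** The printed secondary threshold contradicts its own sentence, the primary endpoint and the entry criterion. This composite is otherwise the stricter of the two: Ba below 0 rather than at or below 0, and single-compartment C below 0 rather than at or below 0. On the multi-compartment apex it becomes the looser one. A program coded from the inequality would give apical credit to an apex that has not moved.

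The retreatment wording matters more because it sits in the primary effectiveness endpoint. Table 11.1-2 schedules POP-Q and PFDI-20 at month 36 for re-operated women, so the data to call a woman a success after a second prolapse operation will exist. Whether she counts depends on how *or* is read. The same composite is tested at 12 months (12.3.8.1), and its earlier-visit values enter the imputation models (12.1.1.3 and 12.3.8.2). The two readings need not be neutral between arms: the hypotheses in 12.3.1 and 12.3.2 look for less intervention for recurrence with mesh.

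**Working it through.** No stated sample size, power or margin is derived from these two rules, so there is no plan figure to reproduce. The check compares the definitions and evaluates each rule.

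**1. Threshold, side by side (multi-compartment apex)**

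| Place | Rule |
|---|---|
| Entry: synopsis, 9.2 | C ≥ -TVL/2 |
| Primary success: synopsis, 7.1 | C < -TVL/2 |
| Secondary success: synopsis, 7.2, 12.1.2 | C < +TVL/2 |

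The primary rule is the exact complement of the apical part of entry. The secondary cut-off lies one full TVL away from it. Positions that pass the printed secondary rule but fail the primary rule satisfy -TVL/2 ≤ C < +TVL/2, and every one of them also meets the apical part of entry.

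The documents give no TVL, so 6, 8 and 10 cm are assumed. Counting whole-centimetre positions:

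| Assumed TVL | Positions passed | Count | At or beyond hymen (C ≥ 0) | Passed by primary rule |
|---|---|---|---|---|
| 6 cm | -3 to +2 | 6 | 3 | 0 |
| 8 cm | -4 to +3 | 8 | 4 | 0 |
| 10 cm | -5 to +4 | 10 | 5 | 0 |

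These are counts of positions, not shares of subjects. The positions at or beyond the hymen would also fail the single-compartment rule in the same bullet (C < 0).

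A subject exactly at C = -TVL/2 satisfies the words but not the primary inequality. Measured against the words instead, the counts are one lower: 5, 7 and 9.

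**2. Retreatment truth table**

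| Surgery in treated segment | Pessary | Literal *or* | Neither allowed |
|---|---|---|---|
| No | No | Success | Success |
| No | Yes | Success | Failure |
| Yes | No | Success | Failure |
| Yes | Yes | Failure | Failure |

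The literal rule fails one pattern of four and the heading's meaning fails three. Surgery only and pessary only change classification.

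**3. Illustration of scale**

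The documents give no rates for these patterns. Assume independent rates s (surgery) and p (pessary). The proportion failing this criterion is 1 - (1 - s)(1 - p) if neither is allowed, and s × p under the literal *or*.

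| s, p (assumed) | Neither allowed | Literal *or* |
|---|---|---|
| 2%, 2% | 1 - 0.98 × 0.98 = 3.96% | 0.04% |
| 5%, 5% | 1 - 0.95 × 0.95 = 9.75% | 0.25% |
| 10%, 5% | 1 - 0.90 × 0.95 = 14.5% | 0.5% |

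The effect on the composite would be no larger than these gaps, because some retreated women would fail another component anyway.

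**4. Reach**

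The sign error touches only the secondary composite, and only multi-compartment subjects. The *or* touches both composites and, through the primary one, the 12-month test and the visit-level outcomes used for imputation.

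**5. A related passage**

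Section 12.3.4 regresses the primary endpoint, within each group, on office-based intervention for recurrence. By 11.5 a pessary is a non-surgical, office-based intervention. If any pessary use is a failure, pessary users have no successes by definition, and part of that covariate is fixed by the endpoint.

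**The case against.** The best reply is that both intentions can be recovered. The inequality is offered as a restatement of the sentence before it, and that sentence is signed correctly in the primary endpoint. The heading of the retreatment criterion excludes the literal *or*, since a re-operated woman cannot sensibly be counted as not retreated. The secondary composite has no hypothesis, margin or sample size of its own. Its other components (Ba below 0, no bothersome bulge, no retreatment) would fail many women whose apex is low. The synopsis also refers to a Statistical Analysis Plan, which may contain derivation rules.

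Much of this stands. The sign is most likely a slip; a sign lost in text conversion is possible but unlikely, since it survives in the primary and entry definitions and is absent all three times here. The position counts describe one component, not composite success. The point about 12.3.4 is peripheral: that regression is supplementary, the covariate is broader than pessary use, and it does not show that pessary users were meant to be successes.

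What does not stand is that nothing needs changing. No supplied text gives a scoring rule that overrides either definition. The documents' use of conjunctions does not settle the matter either: secondary endpoint 6 joins re-intervention and re-surgery with *or* in the synopsis and 12.1.2, but with *and* in 7.2.

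**Conclusion.** Both parts hold. The secondary multi-compartment apical threshold is wrong as written in all three places, displaced by one full TVL. At assumed TVL of 6 to 10 cm, 6 to 10 whole-centimetre apex positions pass it that the primary rule rejects, half of them at or beyond the hymen. The retreatment criterion is ambiguous in all five places, and two of four patterns turn on the reading. The second part is the weightier because it affects the primary effectiveness endpoint. The share of subjects affected and any change in power cannot be derived from the documents; the TVL values and retreatment rates used above are assumptions. This should be fixed before the composites are programmed.

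**What to change.** - In item 7b (synopsis, 7.2, 12.1.2), write the multi-compartment threshold as C < -1/2 TVL. State that the inequality governs at exactly half, since the accompanying words in both composites would admit that value.
- In criterion 3 (synopsis, 7.1) and item 7c (synopsis, 7.2, 12.1.2), replace *or* with *and*. State that either additional POP surgery in the treated segment or any pessary use since the index operation is a failure.
- Program the 12-month composite, the 36-month composite and the visit-level values used for imputation from the corrected text.
- In 12.3.4, say how pessary users are handled in the regression on office-based intervention for recurrence, since they are failures by definition under the corrected rule.

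The cost is wording in the protocol and SAP. No further data are needed and no patient is affected.

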12.1.2.1. Hypotheses

Statistical testing will be performed to determine if the de novo dyspareunia rate of treatment group is non-inferior to the control group. The null hypothesis is that the de novo dyspareunia rate in treatment group is greater than or equal to the rate in control group plus margin:

$$H_0: \pi_{treatment} - \pi_{control} \geq \Delta$$

The alternative hypothesis is:

$$H_a: \pi_{treatment} - \pi_{control} < \Delta$$

where $\pi_{treatment}$ and $\pi_{control}$ are the de novo dyspareunia rate in treatment group and control group respectively, and $\Delta > 0$ is defined as the non-inferiority margin.

Statistical testing will be performed to determine if the AE incidences (pelvic pain, infection, vaginal shortening, atypical vaginal discharge, neuromuscular problems, vaginal scarring, de novo vaginal bleeding, fistula formation and/or de novo voiding dysfunction) rate of treatment group is non-inferior to the control group. The null hypothesis is that the AE incidences rate in treatment group is greater than or equal to the rate in control group plus margin:

$$H_0: \pi_{treatment} - \pi_{control} \geq \Delta$$

The alternative hypothesis is:

$$H_a: \pi_{treatment} - \pi_{control} < \Delta$$

where $\pi_{treatment}$ and $\pi_{control}$ are the AE incidence rates in treatment group and control group respectively, and $\Delta > 0$ is defined as the non-inferiority margin.

The propensity score adjusted confidence intervals described in Section 12.2.3. (Propensity Score Methodology) will be used to summarize the mean score improvement of Quality of Life (PFIQ, PFDI, PISQ, TOMUS pain scale) of the mesh (treatment) group compared to that of the native repair (control) group.

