10.1. Point of Enrollment

Subjects will be considered enrolled in the study once an incision is made in the vaginal wall. All enrolled subjects will have been consented and assigned to receive either the treatment or control procedure per site assignment. All enrolled subjects with a surgery initiated (i.e. incision in vagina) will be considered part of the Intent-to-Treat (ITT) population for the final study analysis. All ITT subjects who undergo the assigned study procedure and had no major protocol deviations will be considered part of the Per Protocol analysis.

The following study timeline (see Table 10.1-1) is based on milestones completed and the current follow-up visit cadence.

Table 10.1-1: Study Timeline

Milestone	Date
Date of study initiation ¹	August 2013
Date of initiation of subject enrollment	October 2013
Date of enrollment completion	December 2016
Expected date of study follow-up completion	December 2019
Expected date of Final Report submission ²	June 2020

¹Study initiation is defined as the date the first study site is “enrollment ready” (i.e. IRB approved, fully executed contract)

²Assuming 6 months from last patient visit completion.

All efforts will be made by site staff to ensure minimal loss to follow-up of patients and will follow a site-specific loss to follow-up plan. These plans will include efforts such as telephone follow-up, Investigator-patient counseling, visit reminder tools, patient stipends if permitted per site budget, and/or other communication methods.

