12.2. General Statistical Methods

12.2.1. Analysis Sets

The Intent-to-Treat (ITT) subject population includes all subjects who provide written informed consent to be enrolled into the study and have a surgery initiated (i.e. incision in vagina) regardless of their adherence with the entry criteria, regardless of treatment and withdrawal/protocol deviations.

The treated population includes all subjects who undergo a study surgical procedure. The subject is defined to have successfully completed the surgical procedure (i.e. prolapse repair successful) and discharged.

The Per Protocol (PP) population includes all subjects in the ITT Population who received the assigned treatment and had no major protocol deviations.

All primary and secondary endpoints will be analyzed on the ITT Population. The primary safety and non-safety endpoints will also be analyzed on the per-protocol population.

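### Secondary safety endpoints, including two non-inferiority tests, are analysed on ITT only, with no analysis by procedure received to show whether non-receipt of mesh has diluted the harm difference

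*Combined protocol and SAP*

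**What the plan says.** Section 12.1.2 describes the secondary endpoints as safety endpoints: "Secondary endpoints will be to evaluate mesh-related complications and subject reported outcomes as safety endpoints between baseline and 36 months". Mesh erosion and mesh exposure come first in its list. Section 12.1.2.1 sets non-inferiority tests for de novo dyspareunia and for the nine-event adverse event endpoint. For the latter, "The null hypothesis is that the AE incidences rate in treatment group is greater than or equal to the rate in control group" plus a margin. Section 12.1.2.2 gives the margins as 7.9% and 8.9%.

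Section 12.2.1 fixes the analysis sets: "All primary and secondary endpoints will be analyzed on the ITT Population". It then adds: "The primary safety and non-safety endpoints will also be analyzed on the per-protocol population". ITT membership is kept "regardless of treatment and withdrawal/protocol deviations". The same section defines a treated population, but assigns no analysis to it, and its definition also calls for a successful repair and discharge.

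Section 10.1 sets the point of entry: "Subjects will be considered enrolled in the study once an incision is made in the vaginal wall". By then women have been "assigned to receive either the treatment or control procedure per site assignment". It also allows for women who do not get what was assigned: "All ITT subjects who undergo the assigned study procedure and had no major protocol deviations will be considered part of the Per Protocol analysis".

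For the co-primary safety endpoint, Section 12.1.1.3 names both the ITT and the per-protocol groups as denominators.

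**The concern.** The sentence that adds per-protocol can be read as covering the primary endpoints of both kinds, or primary safety plus every non-safety endpoint. Secondary safety endpoints are left out on either reading. Nothing in Sections 12.1.2 to 12.1.2.3 supplies a denominator based on the procedure actually done.

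For a harm endpoint tested for non-inferiority, mixing the arms is not conservative. If mesh is truly worse, a woman assigned to mesh who leaves theatre without it, and who has control risk, pulls the difference toward zero and so toward a pass. The plan runs a second set for the co-primary safety test but not for secondary tests of the same form. The usual argument for ITT alone is also weaker here, because there is no random allocation to preserve.

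At stake are the error rate of the two secondary claims and the reading of the erosion and exposure rates, in a study whose secondary objectives (Section 6) include evaluating mesh-related complications.

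**Working it through.** **1. Reproduce the plan's sizes (Section 12.1.2.2).** With equal true rates p, margin M, one-sided 0.05 and 80% power, n per arm = (1.645 + 0.842)² × 2p(1 − p) / M², where the squared term is 6.183.
- Nine-event: 6.183 × 2 × 0.12 × 0.88 / 0.089² = 164.8, so 165, as stated.
- Dyspareunia: 6.183 × 2 × 0.09 × 0.91 / 0.079² = 162.3, so 163, as stated.

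The plan does not state the sidedness of these two tests. One-sided 0.025 would need 210 and 207, so the stated sizes rest on one-sided 0.05, that is, a two-sided 90% interval.

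**2. Dilution model.** Let c be the share of mesh-assigned women who do not receive Uphold LITE. The documents give no value, so c is assumed. Suppose these women carry the control rate and recipients sit exactly at the margin. The ITT mesh rate is then (1 − c)(p + M) + cp, and the ITT difference is (1 − c)M.
- Nine-event, c = 5%: 0.95 × 8.9 = 8.46 points instead of 8.9.
- Dyspareunia, c = 5%: 0.95 × 7.9 = 7.51 points instead of 7.9.

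**3. Chance of falsely declaring non-inferiority.** This is an exact sum over both binomials of the probability that the upper limit of an unadjusted Wald 90% interval lies below the margin, at the stated sizes. Propensity strata are not modelled.

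| c | Nine-event (12% vs 20.9%, 165 per arm) | Dyspareunia (9% vs 16.9%, 163 per arm) |
|---|---|---|
| 0% | 5.1% | 5.5% |
| 2% | 5.6% | 6.0% |
| 5% | 6.4% | 6.8% |
| 10% | 7.9% | 8.3% |

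The excess over 5.0% in the first row comes from the Wald interval, not from dilution. Dilution adds about 0.5 point at 2%, 1.3 points at 5% and 2.8 points at 10%. A normal approximation at 165 per arm, which starts from 5.0%, gives 5.5%, 6.3% and 7.7% (nine-event) and 5.5%, 6.2% and 7.7% (dyspareunia).

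If control women also received mesh at the same rate, the exact figures would be 7.9% and 8.2% at 5%, and 11.6% and 11.9% at 10%.

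**4. Erosion and exposure.** If only Uphold LITE events are counted, the ITT rate is (1 − c) times the rate among implanted women. As an illustration, take 6.5%, the top of the erosion range for anterior repair cited in Section 4. It would read 6.4%, 6.2% and 5.9% at c = 2%, 5% and 10%.

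**5. Power cost of analysing by procedure received** (normal approximation, equal true rates, starting from 165 per arm). Nine-event power goes from 80.0% to 79.1% at c = 5% and 78.1% at c = 10%. Dyspareunia power goes from 80.6% to 79.7% and 78.7%.

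**The case against.** **Non-receipt may be rare.** Enrolment happens at incision, so women who change their minds or are rescheduled never enter ITT. By default a centre enrols one arm only (Section 12.2.2), and surgeons must document at least 10 procedures. What remains is mainly conversion or abandonment during surgery. This stands. It limits the size of the effect, and it makes the two-way figures least plausible at control-only centres, although some centres may enrol both arms.

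**The direction is not guaranteed.** The nine-event endpoint includes procedure-related events. A mesh procedure stopped because of injury or bleeding may carry more of these than a control repair. ITT keeps such events, whereas per-protocol may drop them. This also stands, and it is why per-protocol alone is not a sufficient remedy.

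**A woman without Uphold LITE might be thought unable to have a mesh exposure.** The documents do not support that. Concomitant slings may be synthetic (Sections 8 and 9.1), and exposure is recorded as an adverse event from the pelvic examination (Section 19.2.1) without being limited to the study mesh.

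**Analysis by assigned arm is inferred.** It follows from the ITT label, from membership irrespective of treatment, and from site assignment. No section says in words which arm a converted woman is counted in. That omission is itself worth correcting.

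None of these points supplies the missing analysis. If dilution occurred, no planned analysis of these endpoints would show it.

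**Conclusion.** The gap is in the text: the secondary non-inferiority tests and the erosion and exposure rates rest on ITT alone, while the co-primary safety test has a second set. The change should be made, but the consequence is conditional. It needs some non-receipt of mesh, non-recipients at about control risk, and mesh truly more harmful. On those assumptions the added error is about half a point at 2% non-receipt and becomes material at 5% or more.

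A reader might infer that the tests do exceed their stated 0.05 because of the analysis set. The documents do not support that, because they report no non-receipt rate and the small excess at zero non-receipt belongs to the interval method. A reader might also infer that non-inferiority should be claimed only when two sets agree. The plan does not impose that even on its co-primary safety test, so it is not required here. The stated sample sizes are not in question.

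The non-inferiority tests for office-based and surgical intervention for complications (Sections 12.3.3 and 12.3.4) name no analysis set of their own and share the gap. They use a type I error of 0.025, and no error rate was calculated for them.

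**What to change.** In Section 12.2.1:

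1. State the arm in which a woman is counted under ITT when the procedure done differs from the one assigned.
2. Report Uphold LITE exposure and erosion with women in whom Uphold LITE was implanted as the denominator, and record exposure of sling mesh separately.
3. Alongside ITT, run the dyspareunia and nine-event non-inferiority tests, and those in Sections 12.3.3 and 12.3.4, by procedure actually received among all women with an incision. State in advance how a mesh procedure that was started but stopped without implant is counted, so that its procedure-related events are not lost.
4. Report the number of such women by arm, and report any disagreement with ITT when interpreting a non-inferiority claim.

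Do not use the treated population as now defined, because requiring a successful repair selects on outcome. Do not rely on per-protocol alone.

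The cost is SAP wording, one extra run of existing programs, about 1 to 2 points of power in the by-procedure analysis at 5% to 10% non-receipt, and possibly a slightly less favourable reading on non-inferiority.
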